### **Baseline survey**

Participants will be briefed by a trained research assistant about the purpose and the details of the study, and will be asked to provide written consent. Blocked randomisation will be performed using a centralised online website upon participation. Depending on their group assignment, expectant mothers will be asked to download the respective smartphone app, log in to the app with a unique username and password that they will be assigned. The expectant mothers will also be asked to complete the baseline survey via online, which will take about 15-20 minutes to complete. After that, the participants will be asked about their expected delivery date, and their preferred contact method for the follow-up survey.

Eligible expectant fathers and grandparents who are not present at the clinics will be contacted by the research assistant using the contact methods given by the participating mothers, study details will be explained to them, and they will be asked to provide informed consent. They will be instructed to complete a structured questionnaire, which will take about 15 minutes. Fathers and grandparents who are

allocated to the family-based intervention group will then be provided with a link to download the father or grandparent version of the app, and a unique login information.

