##### ***Exclusion criteria:***

Families will be excluded if the expectant mother scores 10 or higher on the EPDS. Participants will be excluded if the expectant mothers, fathers, or grandparents are not able to understand written or spoken Chinese or are unable/not willing to give informed consent.

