### **Intervention arms**

Participants in the two intervention groups (family-based mHealth intervention and mother-only mHealth intervention) will be granted free and unlimited access to the respective smartphone app from the time of recruitment up to four weeks after childbirth. Their usage of the app will be recorded in terms of the time spent on the app (in minutes). For ethical reasons, the participants in the intervention groups will not be deprived from usual face-to-face antenatal classes at the hospitals; instead, they will be provided something more than they can obtain in existing service.

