### **Ethical consideration**

Approval for the ethics of this study has been obtained from the institutional review boards of the respective institutions. Participation in the study will be completely voluntary. Participants will be reminded that they have the right to terminate their participation at any time during the study, and this will not affect the standard of care they receive at the hospital. All personally identifiable information will be removed before data analysis. In this study, we will obtain information about participants' symptoms of pregnancy depression and PND via the self-reported EPDS at baseline and follow-up. For mothers whose EPDS score is equal to or higher than the cut-off score of 10, we will encourage them to seek help from health and social services. All mothers will receive regular health services and treatments in the hospital as usual. The only difference between the intervention groups and the others will be the use of the mother-only mHealth intervention app or the family-based mHealth intervention app. We will remind mothers that there are relevant services (e.g., the Comprehensive Child Development Service) in the routine hospital care that they can approach when in need.

(vi) **Results analysis**

With regards to **Objective (i)**, we will conduct descriptive analyses to obtain the usage and the coverage of the intervention.

To fulfil **Objectives (ii) and (iii)**, we will conduct general linear model (GLM) to analyse the data. In each GLM, we will use one outcome indicator measured in the follow-up survey as the dependent variable, the corresponding outcome indicator in the baseline survey as the covariate, and the group (family-based mHealth intervention, mother-only mHealth intervention, control [referent group]) as independent variable. We will also conduct sub-group analyses to explore whether the effectiveness of the family-based intervention is affected by various demographic or family factors.

All statistical analyses will be conducted with the intention-to-treat principle. All missing data will be treated with multiple imputation method or full information maximum likelihood depending on the analysis model. Nonetheless, analysis will be performed to compare any baseline differences between dropouts and retained participants. The baseline difference will also be examined by descriptive statistics. SPSS 20.0 will be used, and two-tailed p-values  $< .05$  will be regarded as statistical significance.

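### The mother's baseline survey, including the EPDS that serves as covariate and apparently as eligibility screen, is described after randomisation and app download; state it before allocation

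*Combined protocol and SAP*

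**What the plan says.** The Baseline survey section takes the mother through briefing and written consent, and continues: "Blocked randomisation will be performed using a centralised online website upon participation". The next step is "Depending on their group assignment, expectant mothers will be asked to download the respective smartphone app", with login credentials. The survey follows: "The expectant mothers will also be asked to complete the baseline survey via online". Delivery date and contact preference come after that. Under Intervention arms, app access runs "from the time of recruitment up to four weeks after childbirth".

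Under Exclusion criteria: "Families will be excluded if the expectant mother scores 10 or higher on the EPDS". No time point or screening step is given. Ethical consideration says that depressive symptoms are obtained "via the self-reported EPDS at baseline and follow-up", and adds: "For mothers whose EPDS score is equal to or higher than the cut-off score of 10, we will encourage them to seek help". Section (vi), Results analysis, specifies a general linear model for each outcome with "the corresponding outcome indicator in the baseline survey as the covariate", and commits all analyses to intention to treat.

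Fathers and grandparents who are not at the clinic are contacted later, consent, and complete their questionnaire. Those in the family-based arm receive their app link after the questionnaire.

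**The concern.** The primary outcome is the mother's self-reported EPDS at four weeks postpartum, and its baseline value is the only covariate that the model specification names. A covariate measured before allocation is independent of arm by design. A self-report given after the mother has received her arm's app has no such guarantee. Adjusting for a variable that allocation may have influenced can shift the estimated group difference, and the trial data could not separate such a shift from chance imbalance.

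The second issue is eligibility. If the score that decides eligibility is first seen after randomisation, every score of 10 or more forces a choice the plan does not settle. Keeping the family analyses someone who fails a stated exclusion criterion. Removing the family is a post-randomisation exclusion, which conflicts with the intention-to-treat commitment.

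**Working it through.** This is mainly a question of reading sections against each other.

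1. **Order for mothers.** The sequence in Baseline survey is consent, randomisation, app download by group, questionnaire, then delivery date and contact details. The word *also* in the survey sentence does not mark time, so this order is described but not strictly fixed. Subject recruitment places recruitment and the baseline survey at the first antenatal visit without ordering either against randomisation. The start of app access at recruitment does not settle it, because recruitment and survey share that visit. No section places the mother's survey before allocation.

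2. **Which EPDS can apply the exclusion.** Ethical consideration names two occasions, baseline and follow-up. Follow-up comes after childbirth and cannot determine entry. That leaves the baseline score as the only described score that can do so.

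3. **Timing of exclusions elsewhere.** Section (iii), the contingency plan, places one exclusion explicitly ahead of randomisation: refusal to use a smartphone. Nothing equivalent is said for the EPDS.

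4. **Combining 1 to 3.** If the described order is followed, a score of 10 or more is first seen after allocation. The sentence on encouraging high scorers to seek help covers follow-up as well as baseline and does not mention exclusion, so it does not show when the criterion is applied.

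5. **The covariate.** Results analysis takes the covariate from the baseline survey. By step 1, that value can be collected once the group is known.

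6. **Relatives.** The family is the unit randomised, and randomisation is tied to the mother's participation. A father or grandparent contacted later therefore consents and answers the questionnaire after the family's allocation exists. Those answers are covariates in the Objective (iii) models, and the exclusion criteria also cover a relative's unwillingness to consent. The questionnaire does precede the app link, but the plan does not say whether the group is disclosed before it is completed.

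7. **The plan's own figures.** Inputs from Sample size calculation and Results analysis: d = 0.20, 80% power, two-sided 5% level, 75% retention.
   - Normal approximation: n per arm = 2 × (1.960 + 0.842)² / 0.20² = 392.4 to 392.6, depending on rounding of the quantiles, so 393.
   - t-test version: 393.4, so 394 per arm, and 3 × 394 = 1,182, as stated.
   - Retention: 394 / 0.75 = 525.3, so 526 per arm, and 3 × 526 = 1,578, as stated.

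   Putting eligibility and the survey ahead of randomisation changes none of these figures, provided 1,578 families are randomised.

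8. **Size of bias.** It would depend on how far knowing the group shifts the reported baseline EPDS, and on the baseline-to-follow-up slope. The documents give neither, so no figure is derived.

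**The case against.** The strongest reply is that this is loose drafting, not a faulty design. *Also* is not a time word. Subject recruitment speaks of mothers who are already eligible. The exclusion criteria precede the Randomization section. The smartphone exclusion shows that the authors know exclusions belong before allocation. Any effect on the covariate may be nil, since survey and download occur at one visit and controls also receive information through an app. Results analysis plans a descriptive look at baseline differences, and a separate section lists demographic covariates.

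Much of this stands as evidence of what may be intended, and it limits what can be claimed. It does not remove the point. *Eligible* leaves open how eligibility on the EPDS is established when no earlier EPDS is described. The order of sections is layout, not procedure. The smartphone sentence can equally be read as the one exclusion whose timing was specified. The descriptive comparison may concern only dropouts versus retained participants; even a comparison of arms could not tell a small reporting shift from chance. The demographic list is not carried into the model specification.

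Three stronger readings are tempting and not supported:

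- A reader might infer that the baseline is certainly measured after allocation. The wording leaves the order open.
- A reader might infer that the plan intends to remove randomised families. No section says so.
- A reader might infer a definite loss of power, for example by applying the 26% Hong Kong rate of pregnancy depression from the justification section. That rate is not tied to the EPDS cut-off, and no loss arises unless families are actually removed after allocation.

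**Conclusion.** The point holds as a matter of text, with moderate confidence. The order as described is the weaker one, and no other section corrects it. Followed literally, it collects the self-reported covariate after allocation is known and sets the EPDS exclusion against intention to treat. This rests on two readings: that the Baseline survey paragraph is meant sequentially, and that no EPDS screen exists beyond those described. If either is wrong, only clarification is needed.

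The effect on the estimate cannot be quantified from the documents and may be zero, and no stated sample-size figure is affected. It should still be fixed, because the order as written removes a protection that the design could have at almost no cost, and a baseline already collected in the wrong order cannot be repaired.

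**What to change.** **Mothers (Baseline survey).** State the order within the same visit: consent; EPDS and check against the exclusion criterion; rest of the baseline survey; randomisation; app download. State that this EPDS score is the model covariate. If a separate earlier EPDS screen exists, describe it and say which score is the covariate.

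**Analysis (Results analysis).** State that no randomised family is dropped from analysis because of an EPDS score obtained after allocation.

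**Fathers and grandparents.** For those at the clinic, obtain consent and the questionnaire before the family is randomised. For those contacted later:
- keep the questionnaire before the app link;
- withhold the allocation until it is completed;
- acknowledge that their baseline follows the family's allocation;
- do not remove a randomised family because a relative later declines consent.

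**Cost.** For mothers this is a reordering within one visit, with no new instrument, visit or sample size. Some mothers will complete the 10-item EPDS and then be found ineligible; scoring it first spares them the rest of a 15-20 minute survey. If the team already works in this order, a few sentences are enough.

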### **Implementation of intervention**

The interventions will be implemented at antenatal clinics at KWH and TYH. The interventions will be provided to participants free-of-charge. Families with expectant mothers attending the two clinics will be recruited. For the purpose of intervention evaluation, participants in the intervention groups will receive the intervention. As the interventions will be delivered via smartphone apps, research staff will be stationed at the clinics to assist participants in downloading and installing the apps.

(iii) **Contingency/Alternative Plan if any Problems are Encountered During Implementation**

A potential challenge may come from the non-100% penetration rate of smartphone usage, particularly among older adults. According to the census statistics in Hong Kong, the penetration rate was about 95% in general and 58%-70% among elderly people over 60 years of age. We will encourage the use of smartphones among eligible participants; however, if participants refuse, they will be excluded from our study, before randomisation is performed.

Possible cross-contamination between groups may also be a challenge in this project. To ensure that only participants in the intervention groups can get access to the app, we will provide unique login credentials for each of them. We will also

ask all participants to report their use of the family-based app or other similar parenting apps during the study period.

(iv) **Indicators and Targets**

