### **Randomization**

The RCT will require recruitment of three groups, on a 1:1:1 basis, for comparison: (i) mother-only mHealth intervention; (ii) family-based mHealth intervention; and (iii) health information control. A computerized blocked randomisation programme will be used to generate a series of random numbers to determine the group to which the family is assigned.

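### As written, absent fathers and grandparents are consented and surveyed after the family is randomised, with no concealment of the arm, so their enrolment could differ by arm (minor; cheap to fix)

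*Combined protocol and SAP*

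**What the plan says.** The family is the unit of allocation: under Randomization, random numbers are generated "to determine the group to which the family is assigned".

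The Baseline survey section then gives this sequence:

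1. "Participants will be briefed by a trained research assistant about the purpose and the details of the study", and written consent is taken.
2. "Blocked randomisation will be performed using a centralised online website upon participation".
3. The mother downloads the app for her assigned group and completes her survey online.
4. In the next paragraph: "Eligible expectant fathers and grandparents who are not present at the clinics will be contacted by the research assistant", through details supplied by mothers who are already taking part. Then "study details will be explained to them, and they will be asked to provide informed consent", followed by a questionnaire.
5. Last, relatives "allocated to the family-based intervention group will then be provided with a link to download the father or grandparent version of the app".

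Three other places bear on timing:

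- The inclusion criteria are set for families. They require a smartphone and an email address for each participating member, and willingness to accept the study arrangements.
- The contingency plan, section (iii), says of smartphone use that "if participants refuse, they will be excluded from our study, before randomisation is performed".
- The exclusion criteria remove participants where a mother, father or grandparent is "unable/not willing to give informed consent". They do not say when this is judged, or whether the relative or the whole family leaves.

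**The concern.** Randomisation protects a comparison of fathers or grandparents only if the decision to enter it does not depend on the arm. In the order written, an absent relative decides after the family has been allocated and the mother has her arm's app. The research assistant who makes the approach is not said to be unaware of the arm. The plan describes a father or grandparent app only for the family-based group. Relatives in the other two arms are asked for questionnaires without one, so the incentive to join may differ by arm.

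Hypothesis (ii) compares relatives between arms on anxiety, stress, quality of life and cohesion. If different kinds of relatives enrol in different arms, those contrasts mix the effect of the intervention with selection. The model in section (vi), Results analysis, adjusts for the baseline value of the outcome, which removes only part of such selection. Multiple imputation, full information maximum likelihood and the comparison of dropouts with retained participants are not stated to cover relatives who never enrol and so have no baseline.

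**Working it through.** **Order of events.** The text is silent on two things: whether randomisation waits for absent relatives, and whether anyone is kept unaware of the arm when they are approached. Central randomisation conceals the allocation only until the family is assigned. Giving the app link after the questionnaire keeps a relative's own app use from affecting the baseline scores, but it does not protect the decision to join.

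**The plan's own figure.** With d = 0.20, two-sided 5% and 80% power, a t-based calculation gives 393.4, so 394 per arm, and 3 × 394 = 1,182. Dividing by 0.75 gives 526 per arm (rounded up), and 3 × 526 = 1,578. Both stated totals reproduce and neither is disputed. I use 394 per arm and one relative per family below.

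**Possible size.** The documents give no enrolment rate for relatives, no share absent and no correlations, so every input here is an assumption:

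- 80% of absent relatives join in the family-based arm, and p = 70%, 60% or 50% join in a comparison arm.
- A relative joins when a normally distributed willingness passes a threshold. Willingness has correlation ρ = 0.1 to 0.3 with both the baseline and the follow-up score.
- The baseline to follow-up correlation is r = 0.5 to 0.7.

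Formulas, with φ the normal density and z_p the threshold that lets a proportion p join:

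- All absent: unadjusted bias = ρ × [φ(z_p)/p − φ(z_0.8)/0.8]. The ratio φ(z_p)/p is 0.350 at 80%, 0.497 at 70%, 0.644 at 60% and 0.798 at 50%.
- Half absent, with all present relatives enrolling: replace φ(z_p)/p by φ(z_p)/(1 + p). The number per arm is 394 × (0.5 + 0.5p).
- Adjusted bias b ≈ (1 − r) × unadjusted bias.
- SE = √[(1 − r²)(1/n₁ + 1/n₂)].
- Type I error = Φ(−1.96 + b/SE) + Φ(−1.96 − b/SE).

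Mid-range example, all absent (p = 60%, ρ = 0.2, r = 0.6):

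- Unadjusted bias: 0.2 × (0.644 − 0.350) = 0.059.
- Adjusted bias: 0.4 × 0.0588 = 0.0235.
- Numbers: 394 × 0.6 = 236 and 394 × 0.8 = 315.
- SE: √[0.64 × (1/236 + 1/315)] = 0.0688.
- Type I error: 6.35%.

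| Scenario (p, ρ, r) | All absent: bias, type I error | Half absent: bias, type I error |
|---|---|---|
| Mildest (70%, 0.1, 0.7) | 0.0044 SD, 5.06% | 0.0015 SD, 5.01% |
| Low (60%, 0.1, 0.7) | 0.0088 SD, 5.2% | 0.0026 SD, 5.0% |
| 10-point gap (70%, 0.2, 0.6) | 0.0117 SD, 5.4% | 0.0039 SD, 5.05% |
| Mid-range (60%, 0.2, 0.6) | 0.0235 SD, 6.35% | 0.0069 SD, 5.1% |
| Extreme (50%, 0.3, 0.5) | 0.0672 SD, 13.7% | 0.0166 SD, 5.7% |

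Against the design effect of 0.20 SD, the mid-range bias is 0.0235/0.20 = 12% if all are absent and 0.0069/0.20 = 3% if half are. The bias can run in either direction.

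**The case against.** The best counter-argument is that the family's membership is largely settled before allocation. The inclusion criteria define eligible families, with requirements on each participating member and a willingness condition, and family eligibility would normally be checked before a family is randomised. The Baseline survey section contacts relatives it already calls eligible. Its opening sentence has participants briefed and consenting, and elsewhere that word covers relatives. The contingency plan places smartphone refusal, a concern it raises chiefly for older adults, before randomisation. On this view the second paragraph of the Baseline survey section describes a different group of people, not a later time.

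This has weight. The timing is inferred from the order of the text, and some relatives may well be identified and agreeable beforehand. But none of these places says that absent relatives consent or complete baseline before randomisation, and their consent step is described separately, after allocation.

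Three stronger readings are tempting and are not supported:

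- **That relatives' baseline scores are contaminated by their own app use.** The app link comes only after their questionnaire.
- **That the maternal primary outcome is biased.** That needs the exclusion criteria to mean that a relative's refusal after randomisation removes the whole family. The sentence speaks of participants where the one before it speaks of families, which leans towards removing the individual, though not conclusively.
- **That error rates near 13.7% are to be expected.** That figure needs every input at its worst and no relative present at the clinic.

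**Conclusion.** The point stands as a minor one. The plan leaves absent relatives' enrolment unprotected: as ordered, it follows randomisation, and no concealment of the arm is described. Differential enrolment could therefore bias the relatives' secondary comparisons in hypothesis (ii). The documents do not show that it will.

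Across the assumed inputs the adjusted bias runs from about 0.004 to 0.067 SD if all relatives are absent and from 0.0015 to 0.017 SD if half are. These ranges rest wholly on the assumed participation gap and correlations. With equal enrolment and equal selection in each arm, the bias from this source is zero. Confidence is medium, because the order of events is read from the text and not stated in it.

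**What to change.** In the Baseline survey section:

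1. Have the mother list all eligible relatives before the family is randomised.
2. Obtain relatives' consent and baseline before randomisation where feasible. Otherwise approach them with one arm-neutral script, and do not disclose the arm until consent and baseline are complete. The app link is already held back until then, so only the disclosure of the arm needs adding.
3. Report relatives' enrolment by arm, with all listed relatives as the denominator. Without a list made before randomisation, that denominator cannot be reliably recovered later.

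Reconcile the contingency plan, the inclusion criteria, the exclusion criteria and the Baseline survey section on timing. State that a relative's refusal after randomisation removes only that relative, so that the mother stays in the intention-to-treat analysis.

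The cost is a short listing step at the clinic, one common script and some delay for some families. Masking will be incomplete, because the mother may reveal her arm. Randomisation need not wait for every relative, so on-site help with installing the mother's app can continue.
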